14.0 Potential Benefits to Participants

Whereas no assurance can be made to an individual subject that he/she will personally benefit from such research, the experience should not impose any significant risk. Subjects will have the opportunity to learn about factors that may be associated with cigarette smoking. Quitting tobacco will be strongly recommended to our subjects and cessation materials will be provided. Referrals to community resources will also be made.

15.0 Statistical Considerations

15.1 Data Analysis Plan

The goals of this study are: to determine the effect of switching to SREC on biomarkers of exposure and effect (assessed at 4 and 6 weeks); to determine levels of salivary NNN and HPB-releasing DNA adducts in SREC users (assessed in the verified complete switchers at weeks 4 and 6); and to determine important moderators for SREC use and exposure/effect measures.

Demographic and smoking history variables will be summarized and compared to national survey data for the general population of smokers. Baseline covariates will be summarized to inform the comparison data retrieval on non-users of nicotine/tobacco and smokers from recently completed studies. Continuous measures will be summarized by mean (SD), median (range) or other summary measures. The distribution of biomarker and cytokine levels is usually highly right-skewed and will be analyzed in the log scale and reported as geometric means and 95% confidence intervals. Categorical covariates will be summarized by contingency tables.

The primary endpoints are the weeks 4 and 6 for (1) toxicant and carcinogen exposure biomarkers; (2) inflammatory biomarkers; and (3) DNA adducts adjusted for the baseline value. The analysis of our primary endpoints will use linear mixed models to account for potential intra-subject correlation due to repeated measurements at 4 and 6 weeks from a single individual. With two repeat observations, the within subject correlation structure will be compound symmetry. Residual plots and other diagnostic methods will be used to check model assumptions. The mean model for each hypothesis will include the overall mean and an effect for time (4 or 6 weeks). Therefore, our primary analysis for all endpoints will only adjust for the baseline biomarker level (for precision). Due to the multiple biomarkers being tested in this exploratory trial, a reduced alpha level of 0.001 will be used to determine statistical significance for the time effect. An additional analysis will be completed adjusting for important factors such as environmental toxicant exposures, stress and health to determine the effect their inclusion has on the association between group and biomarkers. The secondary endpoints include the amount of product

used (cigarettes per day, number of e-cigarette episodes and puffs per day and the number of smoke-free days (cigarette avoidance). These outcomes are considered counts and will be analyzed as Poisson or negative binomial variables. Product use by visit will be analyzed by generalized estimating equation (GEE) models, which account for the multiple visits for each individual. Smoke-free days across the entire study period (approximately 42 days) will be analyzed by a Poisson or negative binomial regression. These analyses will include an offset term to adjust for the number of days reported by visit and in total. Covariates will include baseline patient characteristics that may affect patterns of use. Exploratory endpoints include the subjective measures which will be collected up to 6 times during the study period. Measures providing a score will be analyzed using a linear mixed model. The fixed effect is visits. AEs and SAEs (safety endpoints) will be tabulated. Compliance to the assigned treatment is a concern and we are considering the possibility that the non-compliance rate could be as high as 50%, despite our efforts to keep it at low as possible. Complete switching will be biochemically verified; therefore the analysis will be repeated with only those identified as completely switching to SREC. Estimates and confidence intervals of the degree of reduction in outcome variables can be determined for those that successfully switched to the study product. In addition, we will summarize compliance and evaluate the correlation between compliance and baseline covariates to identify potential predictors of treatment compliance. Finally, we will complete a sensitivity analysis that accounts for missing information using multiple imputation with the Markov Chain Monte Carlo (MCMC) method carried out in PROC MI in SAS. Missing values are imputed using regression models developed from baseline covariates. Values can be imputed for both continuous and categorical variables.¹⁰⁴ Following imputation, standard statistical methods can be applied. A final single assessment of time effect will be obtained from combining the results across the imputed datasets using PROC MIANALYZE in SAS.

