- HMPMA: 4-hydroxybut-2-ylmercapturic acid
- 2-HPMA: 2-Hydroxypropylmercapturic acid
- 3-HPMA: 3-Hydroxypropylmercapturic acid
- HR: Heart rate
- ITP: Investigational Tobacco Product
- ITR: Interactive Text Response
- ITRS: Interactive Text Response System
- NIDA: National Institute for Drug Abuse
- NMR: Nicotine metabolite ratio
- NNAL: 4-(Methylnitrosamino)-1-(3-pyridyl)-1-butanol
- NNN: *N*-Nitrosonornicotine
- PAH: Polycyclic aromatic hydrocarbons
- PheT: Phenanthrene tetraol
- PS-ECDI: Penn State Electronic Cigarette Dependence Index
- SAE: Serious adverse event
- SREC: Standardized Research E-cigarette
- TNE: Total Nicotine Equivalents
- VOC: Volatile organic compounds

PROTOCOL TITLE: Biomarkers in SREC Users

VERSION DATE: 03/13/2024

STUDY SUMMARY

| | |
|---|---|
| Study Title | Biomarkers of Exposure and Effect in SREC Users |
| Study Design | Within-subjects, repeated measures study |
| Primary Objective | Measure biomarkers of tobacco constituents and inflammation in smokers who will switch for six weeks to the Standardized Research E-cigarette (SREC) developed by the National Institute on Drug Abuse. |
| Secondary Objective(s) | Collect and analyze information on behavioral aspects and a comprehensive panel of subjective measures, including patterns and topography of SREC use. |
| Research Intervention(s)/Investigationa l Agents | Standard Research E-cigarette (SREC) developed by the National Institute on Drug Abuse |
| IND/IDE # (if applicable) | IU0000806, IU0000807, IU0000935, IU0000937, IU0000939/P00128 |
| Investigational Drug Services # (if applicable) | NA |
| Study Population | Cigarette smokers |
| Sample Size (number of abstinent completers) | 30 |
| Study Duration for Individual Participants | A total 11 weeks: 1 week baseline period, 6 weeks of assigned product use and a follow-up at week 10 |

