15.2 Power Analysis

Based on our previous experience, we estimate the inter-subject coefficient of variation (CV) for the biomarkers listed in Table 1 to be between 30% and 40%. Biomarkers will be analyzed in the logarithmic scale; as a result, the standard deviation (SD) of the log of the level of these biomarkers is approximately equal to the CV in their original scale. For purposes of our power calculations, we will set the SD for each biomarker at 0.4 and assume a correlation of 0.5 between baseline and 6-week biomarker levels. The major hypotheses will be tested including only smokers who completely switch from smoking to SREC use. If a conservative estimate of only 50% of the 30 enrolled subjects achieving complete switching to SREC is applied, then 15 subjects would have greater than 90% power to detect a 45% decrease in the biomarker level in 6 weeks with a paired t-test. However, we incorporated measures to maximize the complete switching (as described in the Study procedures section) and will aim to have at least 20 subjects achieving this goal. The significance level was set at 0.001 due to multiple biomarkers being tested.

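### Baseline adjustment adds no precision in this single-arm study, and if the degree of reduction is read from the adjusted model its confidence interval is too narrow

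*Combined protocol and SAP*

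**What the plan says.** The Study Summary describes a "Within-subjects, repeated measures study", and there is no comparison arm. Section 3.2 says percentage change from baseline will be assessed for all biomarkers.

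Section 15.1 specifies a linear mixed model on the log scale. Its mean structure is given as "The mean model for each hypothesis will include the overall mean and an effect for time (4 or 6 weeks"). Baseline is not one of the responses: "With two repeat observations, the within subject correlation structure will be compound symmetry". Baseline enters as a covariate: "our primary analysis for all endpoints will only adjust for the baseline biomarker level (for precision"). The significance level is attached to one parameter: "a reduced alpha level of 0.001 will be used to determine statistical significance for the time effect".

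For verified switchers, section 15.1 adds: "Estimates and confidence intervals of the degree of reduction in outcome variables can be determined for those that successfully switched to the study product". It does not say from which model or with which standard error.

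Section 15.2 bases power on a paired t-test of baseline against week 6, also at 0.001: "we will set the SD for each biomarker at 0.4 and assume a correlation of 0.5 between baseline and 6-week biomarker levels". It states more than 90% power with 15 switchers for a 45% decrease.

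**The concern.** Adjusting for baseline improves precision when groups are compared, because it removes between-person variation from the contrast. Here there is nothing to compare between groups. The quantity of interest is the follow-up mean minus the baseline mean, and the baseline mean is itself an estimate from the same few people, each contributing one first-morning urine at Baseline 2.

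A model with baseline only as a covariate conditions on the observed baseline values. Its standard error for the adjusted follow-up mean therefore contains no sampling error for the baseline mean. If an analyst subtracts the baseline mean as a known number and keeps the model's standard error, a sample whose baseline ran high by chance has its regression to the mean counted as an effect of switching.

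The study aims to supply reference data on SREC (section 1.0), so the width of these intervals is part of its main product. The test matters most for biomarkers that may hardly move. Section 2.0 reports near-identical medians in e-cigarette users and smokers for 8-iso-PGF2α (0.80 and 0.80 pmol/mL) and PGEM (32.1 and 31.4 pmol/mL).

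**Working it through.** **Inputs.** From section 15.2: log-scale SD 0.4, correlation ρ = 0.5, α = 0.001, n = 15 (pessimistic), 20 (target) and 30 (all enrolled). Assumptions not in the documents: a two-sided test, and the same SD at follow-up as at baseline; both the SD ratio and ρ are varied below.

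**1. The plan's own power figure.**
- SD of the paired log difference = 0.4 × √(2(1 − 0.5)) = 0.40.
- A 45% decrease is ln 0.55 = −0.598.
- Noncentral t with 14 degrees of freedom, two-sided 0.001, n = 15: power 0.912. The stated figure of more than 90% is reproduced.

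**2. Does the covariate add precision?** With complete data, the adjusted mean at the average baseline equals the raw follow-up mean. The estimated reduction is therefore the mean paired change with or without the covariate. In the week 6 minus week 4 contrast, baseline cancels within each person. A mixed-model fit to one simulated data set of 20 people gave the same contrast and the same standard error (0.0649) both ways.

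**3. Variance of the reduction** (s₀, s₁ = SDs at baseline and follow-up).
- Correct: (s₀² + s₁² − 2ρs₀s₁)/n.
- From the adjusted model, baseline mean treated as fixed: s₁²(1 − ρ²)/n.
- Omitted: (s₀ − ρs₁)²/n, which is never negative.

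At the plan's inputs the numerators are 0.16 (correct), 0.12 (model) and 0.04 (omitted). The standard error ratio is √(0.12/0.16) = 0.866, or about 13% too small. At n = 15 the standard errors are 0.089 (model) and 0.103 (correct).

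**4. Consequence for tests and intervals.** With r the standard error ratio, actual α = 2·P(t₍ₙ₋₂₎ > t_crit × r). Coverage follows in the same way from the 0.05 critical value.

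| n | Actual error at nominal 0.001 | Same, 1,000,000 simulated trials | Paired t, simulated | Coverage of nominal 95% CI |
|---|---|---|---|---|
| 15 | 0.0029 | 0.0029 | 0.0010 | 91.6% |
| 20 | 0.0032 | 0.0033 | 0.0010 | 91.5% |
| 30 | 0.0036 | 0.0035 | 0.0009 | 91.3% |

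Regressing the change score on centred baseline gives the same error rates (0.0029, 0.0032, 0.0036). The simulated error for the week 4 versus week 6 contrast stays at 0.0010.

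**5. Sensitivity at n = 15, nominal 0.001.**

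| Varied | Actual error |
|---|---|
| ρ = 0.3 / 0.5 / 0.7 / 0.9, equal SDs | 0.0047 / 0.0029 / 0.0019 / 0.0012 |
| Follow-up SD 0.75 / 1 / 1.25 / 1.5 / 2 times baseline, ρ = 0.5 | 0.0095 / 0.0029 / 0.0016 / 0.0012 / 0.0010 |

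The omitted term vanishes when s₀ = ρs₁, which at ρ = 0.5 means a follow-up SD twice the baseline SD.

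**6. Effect on an interval.** For a 45% fall at n = 15, the log-scale half-widths are 0.193 (model: 2.160 × 0.0894) and 0.222 (paired: 2.145 × 0.1033). Back-transformed, the intervals are falls of 33-55% and 31-56%.

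**The case against.** The strongest reply is that the plan never commits to the faulty calculation. Section 15.1 only says that reduction estimates and intervals can be obtained. The one baseline-to-follow-up test named anywhere is the paired t-test in section 15.2, for the same switchers and at the same 0.001, and that test is sound. This stands: the under-coverage is conditional on reading the reduction from the adjusted model. It does not dispose of the point, because that model is the only primary analysis section 15.1 specifies, and the paired test appears only under power.

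A reader might infer three stronger things that the documents do not support.

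- *That the 0.001 level set in section 15.1 is itself inflated.* Section 15.1 attaches it to the time effect, with time coded as week 4 or 6. That contrast keeps its level.
- *That the error is 0.003 or more for every biomarker.* The documents give no follow-up SD and no biomarker-specific correlation. Depending on these, the error can be close to 0.001 or well above 0.003.
- *That the section 15.2 power is wrong.* It already uses the paired variance and is reproduced.

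Two further points are fair. With missing week 4 or 6 values, a baseline covariate can recover a little information, so the statement that it adds no precision is limited to complete data. And the practical effect is often small. In Table 1, every listed marker other than 1-HOP fell by at least 53%; at the correct standard error of 0.103 that is about 7 standard errors (−ln 0.47 = 0.755; 0.755/0.103 = 7.3). Even at 0.0036 each, the eight Aim 1 biomarkers in Table 2 sum to 8 × 0.0036 = 0.029.

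**Conclusion.** The point holds in conditional form and should be fixed. The stated reason for the covariate is not valid for complete single-arm data, and the natural route from the stated model to the promised reduction gives intervals that are too narrow.

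The size rests on a log-scale SD of 0.4 at both times, correlation 0.5, a two-sided test, and the baseline mean being treated as fixed. It would change few conclusions about large falls in exposure biomarkers. It matters for the coverage of the published reference intervals and for biomarkers of effect that may be near null.

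**What to change.** In section 15.1, replace the baseline-adjusted model as the source of the reduction estimates by one of these:

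- (a) each person's log ratio to baseline at weeks 4 and 6 as the response, with no baseline covariate; or
- (b) a mixed model with baseline as a third response, unstructured covariance, and week-minus-baseline contrasts. This also uses the correlation with baseline when a week 4 or 6 value is missing.

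Report geometric mean ratios with confidence intervals from that model. State that the baseline-to-follow-up contrast carries the 0.001 level, in line with section 15.2. Keep baseline as a covariate only for the separate question of whether the starting level predicts the size of the fall.

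The cost is a change of wording. Intervals become about 15% wider at correlation 0.5 (0.222/0.193 = 1.15 at n = 15). No extra participants or samples are needed, and power at n = 15 stays at 0.912.

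### Section 15.1 attaches alpha 0.001 to a time effect that is week 6 minus week 4, not to the change from the smoking baseline that the hypotheses state and Section 15.2 powers

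*Combined protocol and SAP*

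**What the plan says.** Four statements in Section 15.1 fix what the time effect is.

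- The linear mixed model is there to handle repeated values at weeks 4 and 6 from the same person, and "With two repeat observations, the within subject correlation structure will be compound symmetry".
- "The mean model for each hypothesis will include the overall mean and an effect for time (4 or 6 weeks", so time has two levels and baseline is not one of them.
- Baseline enters only as a covariate: "our primary analysis for all endpoints will only adjust for the baseline biomarker level (for precision".
- The decision rule is that "a reduced alpha level of 0.001 will be used to determine statistical significance for the time effect".

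The multiple-imputation paragraph repeats the target: "A final single assessment of time effect will be obtained from combining the results across the imputed datasets". For verified complete switchers, 15.1 adds that "Estimates and confidence intervals of the degree of reduction in outcome variables can be determined", with no test or alpha attached.

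The rest of the plan asks about change from the smoking baseline. Primary Aim 1 (Section 1.0) compares exposure with baseline while smoking and hypothesises significant reductions. Section 3.1 makes changes at 4 and 6 weeks after switching the primary endpoint, and Section 3.2 expresses change as a percentage of baseline. Section 15.2 states that "The major hypotheses will be tested including only smokers who completely switch from smoking to SREC use" and claims over 90% "power to detect a 45% decrease in the biomarker level in 6 weeks with a paired t-test", also at 0.001, using a correlation between baseline and week 6.

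**The concern.** The only significance rule in the analysis section belongs to a contrast that no hypothesis mentions. A marker that falls steeply by week 4 and stays down satisfies the null hypothesis of the 15.1 test, so a large and sustained reduction would be reported as not significant. A significant result would show only that levels moved between weeks 4 and 6.

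Early falls are plausible for some markers. In the two switching studies in Table 1, 3-HPMA was 14% of baseline at 5 days and 44% at 2 weeks, and HMPMA was 13% and 33%. This does not hold for every marker. 1-HOP was 96% of baseline at 2 weeks. NNAL was 35% at 2 weeks, against an estimated 1.3% of smokers' levels in longer-term users, so it may still be falling at week 4. The Background also warns that these study designs differ. The concern does not depend on a plateau, because the contrast is the wrong one whatever the time course.

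**Working it through.** **Inputs from Section 15.2.** SD of the log biomarker 0.4; correlation between baseline and week 6 of 0.5; alpha 0.001; n = 15 under 50% switching, 20 as the target, 30 in all; effect a 45% decrease.

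**Assumptions not in the plan.** The test is two-sided. The correlation r between weeks 4 and 6 lies between 0.3 and 0.9.

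**Step 1: reproduce the plan's figure.**
- Effect: ln(0.55) = −0.598.
- SD of the paired difference: 0.4 × √(2 × (1 − 0.5)) = 0.4.
- Noncentrality at n = 15: 0.598 / (0.4/√15) = 5.79, on 14 df, with critical value 4.14.
- Power from the noncentral t: 91.2% (n = 15), 99.2% (n = 20), above 99.9% (n = 30). One-sided at n = 15 it is 95.3%.

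The claim of more than 90% holds for the baseline to week 6 contrast.

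**Step 2: identify the 15.1 time effect.** With two complete post-switch values per person, a person-level baseline covariate shifts both values equally and cancels from the week 6 minus week 4 difference. Mixed models fitted to three simulated data sets (n = 15) gave time-effect t statistics of 0.799, −0.661 and −0.713. The paired week 6 versus week 4 t statistics were the same to four decimals. The baseline to week 6 t statistics in those data sets were −5.14, −5.13 and −5.36.

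**Step 3: power of that contrast.** The SD of the difference is 0.4 × √(2 × (1 − r)), with n − 1 df and alpha 0.001.

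*Fall reached by week 4 and held.* The true difference is zero, so the rejection rate is 0.1% at any n and for any size of fall. Simulation of a held 45% fall gave 0.09% to 0.11%.

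*Fall deepening between weeks 4 and 6.* These scenarios are illustrative. The differences are ln(0.35/0.40) = −0.134 and ln(0.55/0.60) = −0.087. Ranges run from r = 0.3 to r = 0.9.

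| Scenario | n = 15 | n = 20 | n = 30 |
|---|---|---|---|
| 60% to 65% | 0.85% to 17.7% | 1.4% to 33.9% | 3.0% to 66.2% |
| 40% to 45% | 0.4% to 4.1% | 0.5% to 7.9% | 0.9% to 19.2% |

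For example, for 60% to 65% at n = 15 and r = 0.5, the noncentrality is 0.134 / (0.4/√15) = 1.29 and power is 1.3%. In the same 60% to 65% scenario the baseline to week 6 contrast exceeds 99.9% at each n.

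*Further fall after week 4 needed for 90% power (r = 0.3 to r = 0.9).* 50% to 23% at n = 15; 43% to 19% at n = 20; 35% to 15% at n = 30.

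**The case against.** The strongest reply is that the intent is plain. Section 15.2 says how the major hypotheses will be tested, names a paired t-test on the 6-week decrease, and gives 0.001 for the same reason as 15.1. An analyst who reads both sections would probably test the right thing. That stands as evidence of intent. It does not settle which section governs: 15.1 defines the primary analysis, 15.2 justifies the sample size, and they give the same alpha to different contrasts. The choice should not be left until the data are in.

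A second reply is that the overall mean in the model could be the reduction from baseline. That would be so if the outcome were coded as log change and the baseline covariate were centred. Section 15.1 states neither and gives the overall mean no alpha.

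A third is that time effect may be loose wording for the effect of switching. Section 15.1 also refers to an association with group in a single-group study, so wording may have been carried over. The two-level definition of time, the count of two repeats and the covariate role of baseline all argue against that reading, and the imputation paragraph repeats the term.

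Finally, the plan calls the trial exploratory and will report geometric means with 95% confidence intervals, so the reductions would still be visible. That limits the harm. But the plan also sets a significance threshold and sizes the study on it, and the threshold should sit on the hypothesis.

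It is fair to add that the ranges in the table depend heavily on a correlation the documents do not give. The decisive figure, 0.1% for a held fall, does not depend on it.

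**Conclusion.** The concern holds and must be fixed. As written, 15.1 tests week 6 against week 4 at 0.001 and specifies no test of the change from baseline. The power stated in 15.2 is correct for its own contrast but does not carry over to the 15.1 test: 91.2% becomes 0.1% at n = 15 when a 45% fall is held from week 4. The identification of the contrast follows from the text and needs no numerical assumption. The 91.2% assumes a two-sided test. The figures for a deepening fall also rest on the assumed week 4 to week 6 correlation and on the chosen scenarios. The intended contrast can be inferred from 15.2, so this is a repairable contradiction and not a flaw in the design or sample size.

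**What to change.** In Section 15.1, attach alpha 0.001, stated as two-sided, to the log change from baseline to week 6, matching 15.2. Either of two tests will serve:

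- the paired t-test; or
- a repeated-measures model with baseline, week 4 and week 6 as outcomes, visit as a factor, unstructured covariance and a small-sample degrees-of-freedom method such as Kenward-Roger.

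With complete data the two give the same test on n − 1 df. A large-sample z test should be avoided: at n = 15 and nominal 0.001 its true size is 0.54%.

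Report the baseline to week 4 change alongside, both as ratios of geometric means with confidence intervals, and make week 6 versus week 4 secondary. In the imputation paragraph, replace the time effect with the same baseline contrast.

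Sections 3.1 and 15.1 name both weeks without ranking them; week 6 is proposed because 15.2 powers it. If both weeks are to carry alpha, the plan should say so. Splitting to 0.0005 each gives 85.2% power per contrast at n = 15 and 98.2% at n = 20, taking a correlation of 0.5 for each. The average of weeks 4 and 6 against baseline is a further option. With all correlations 0.5, its SD is 0.4 × √(1 + 0.75 − 1) = 0.346 and power at n = 15 is 98.0%.

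The cost is SAP wording and a few lines of code. Baseline, week 4 and week 6 samples are already scheduled (Section 5.1 and Table 3), so no visits, data or participants are added.

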Primary Aim 1: To analyze a panel of exposure biomarkers in the urine of smokers switched to SREC and compare the exposure profiles against baseline measures (while smoking) and the available data on the levels of these biomarkers in non-users of tobacco/nicotine products. The biomarkers will include total nicotine equivalents (TNE, biomarker of nicotine), total NNAL and total NNN (TSNA biomarkers), PheT (PAH biomarker), and mercapturic acids HMPMA, 2-HPMA, and 3-HPMA (biomarkers of VOC).

Hypothesis: There will be significant reductions in exposure in switchers to SREC, to the levels typically found in non-users of nicotine/tobacco products.

Secondary Aim 1: To compare formaldehyde-DNA adducts and oxidative DNA adduct 8-oxo-dG in DNA from oral cells and leukocytes, a comprehensive panel of circulating cytokines and chemokines, and the urinary biomarkers of oxidative damage and

inflammation 8-iso-PGF-2 α and PGEM in smokers switched to SREC against the baseline levels and the available data on non-users of nicotine/tobacco products. In a subset of study participants, a comprehensive panel of circulating cytokines and chemokines will be also analyzed in plasma.

Hypothesis: The levels of biomarkers of effect in SREC switchers will be lower than at baseline (while smoking cigarettes), but higher than those found in non-users of nicotine/tobacco.

Secondary Aim 2: To analyze salivary NNN and the NNN-derived HPB-releasing DNA adducts in oral cell in smokers who completely switch to SREC, and compare to baseline measures (while smoking) and the available data on the levels of these biomarkers in non-users of tobacco/nicotine products. Only verified switchers to SREC (as determined by analyzing urinary biomarkers in Aim 1) will be included in these analyses.

Hypothesis: Levels of salivary NNN and HPB-releasing DNA adducts will be lower after switching to SREC than at baseline, and higher than in non-users of nicotine/tobacco.

For all Aims, data on the levels of biomarkers in non-users of tobacco/nicotine products will be retrieved from our recently completed study. In addition, data on smokers from the same study will be used as a reference, to verify that baseline levels of biomarkers assessed in our participants in Aims 1-3 are representative of the typical levels found in smokers.

Collectively, this study will contribute to better understanding of the long-term health effects that may be associated with e-cigarette use.

[figure not shown]

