5.0 Procedures Involved

5.1 Study Design

Smokers will be asked to completely switch to SREC for 6 weeks. Study participants will be assessed at baseline and weeks 1, 2, 3, 4, and 6 for complete switching from cigarettes to SREC, as well as SREC use patterns and subjective measures. The potential changes in the levels of various toxicant and carcinogen exposures, inflammatory biomarkers, DNA adducts, and oral NNN formation will be assessed at baseline and at 4 and 6 weeks. The proposed clinical trial procedures and measures have been used in a number of studies we have conducted.¹⁰¹⁻¹⁰³

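### The supplementary adjusted analysis targets a group effect that the single-arm model does not contain, and using the week 4 versus week 6 effect instead would not address change from smoking baseline

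*Combined protocol and SAP*

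**What the plan says.** The Study Summary gives the design as "Within-subjects, repeated measures study", and Section 5.1 has a single course for everyone: "Smokers will be asked to completely switch to SREC for 6 weeks".

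Section 15.1 sets out the primary mixed model: "The mean model for each hypothesis will include the overall mean and an effect for time (4 or 6 weeks"). It adds that "our primary analysis for all endpoints will only adjust for the baseline biomarker level (for precision"), that "With two repeat observations, the within subject correlation structure will be compound symmetry", and that "a reduced alpha level of 0.001 will be used to determine statistical significance for the time effect".

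The same section then announces a further analysis that adds environmental exposure, stress and health as covariates. Its purpose is to determine "the effect their inclusion has on the association between group and biomarkers". It does not say whether these factors enter as baseline values, as other person-level values, or as values that change between visits.

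Table 3 gives the schedule of the relevant instruments:

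- Environmental Tobacco Smoke Exposure, and Occupational & Environmental Toxicants: Baseline 2 and week 4 only.
- Respiratory and Global Health: Baseline 2 and weeks 1, 2, 3, 4 and 6.
- CESD: screening, week 4 and week 6.
- No instrument is labelled as a measure of stress.

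Other people enter the plan only as reference data. Section 1.0 says that "data on the levels of biomarkers in non-users of tobacco/nicotine products will be retrieved from our recently completed study", and smokers from the same study are used to check that the baseline levels are typical.

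**The concern.** An adjusted analysis is read by comparing an effect before and after adjustment. Here the named effect is not in the model, so an analyst would have to choose a substitute, and the natural one is the time effect that Section 15.1 tests. That effect compares week 4 with week 6, both after the switch.

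With no concurrent control, a reader will want to know whether something other than SREC, such as less secondhand smoke at home or a change at work or in health, accounts for part of the fall from smoking baseline. I find no other analysis in Section 15.1 that takes this up: the complete-switcher repeat concerns compliance, and the multiple imputation concerns missing data. If the adjusted and unadjusted time effects agree, the agreement could be reported as robustness when for some covariates it follows from the arithmetic alone.

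**Working it through.** **The plan's own figure.** The adjusted analysis has no figure of its own. The power statement in Section 15.2 shows which quantity the plan treats as important. Inputs: log-scale SD 0.4, correlation 0.5, n = 15, a 45% decrease, alpha 0.001 (two-sided assumed).

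- SD of the paired difference = sqrt(2 × 0.4² × (1 − 0.5)) = 0.4.
- Effect = |ln 0.55| = 0.598.
- Non-centrality = 0.598 / (0.4/√15) = 5.79 on 14 df.
- Power from the non-central t = 91.2%, which agrees with the stated figure of more than 90%.

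That calculation concerns change from baseline to week 6, not week 4 against week 6.

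**Algebra.** For person i at visit j, let y_ij = μ + τ·[j = week 6] + β·b_i + γ·x_i + u_i + e_ij, where b_i is the baseline biomarker and x_i a covariate with one value per person. The within-person difference is y_i6 − y_i4 = τ + (e_i6 − e_i4). The terms μ, β·b_i, γ·x_i and u_i all cancel. With both visits present and compound symmetry, the estimate of τ is the mean of these differences, so adding x_i cannot change it.

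**Which covariates this covers.** The two environmental scores have one pre-switch and one post-switch value. The baseline value, the week 4 value and the change between them are each a single number per person. Carrying week 4 forward to week 6 also gives one number per person. Treating the week 6 score as missing and using complete rows would remove every week 6 row.

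**Simulation check.** Random-intercept REML models were fitted to 200 simulated data sets at each sample size. The table shows the change in the time coefficient (log scale) when the covariate is added.

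| Situation | n = 15 | n = 20 | n = 30 |
|---|---|---|---|
| Person-level covariate, complete data: largest change | <1e-15 | <1e-15 | <1e-15 |
| Person-level covariate, about 20% of week 6 missing, depending on the covariate: mean absolute (largest) | 0.024 (0.164) | 0.023 (0.152) | 0.021 (0.093) |
| Covariate measured at weeks 4 and 6, complete data: mean (largest absolute) | −0.158 (0.429) | −0.150 (0.421) | −0.148 (0.474) |

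The first row is algebraic. The other two rest on assumed covariate effects (0.2 and 0.3 per SD) and an assumed shift of 0.5 SD between weeks 4 and 6. A shift of −0.15 is a ratio of exp(−0.15) = 0.86.

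In one data set with n = 20, the time coefficient was 0.1249 both without and with the person-level covariate. The intercept went from −0.560 to −0.564, and to −1.184 when 3 was added to the covariate, so its position depends on coding. A time-varying covariate moved the time coefficient to −0.068.

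Making baseline a third time point does not help a person-level covariate: the week 4 and week 6 effects were −0.7439 and −0.5785 before and after adjustment.

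**What a model for change can show.** Let log(visit/baseline) = δ + γ·Δx, where Δx is the change in exposure score. The unadjusted mean is δ + γ·mean(Δx). With Δx coded so that zero means no change, the intercept is δ. With Δx centred at its mean, the intercept is again δ + γ·mean(Δx). In a simulated case where the whole fall came from reduced exposure and SREC had no effect, the unadjusted mean was −0.67 (ratio exp(−0.67) = 0.51), the intercept at zero change was −0.09 (ratio 0.91), and centring returned −0.67.

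**The case against.** A reader might infer that the planned analysis is bound to show no influence of these factors, whatever the truth. The documents do not support that, for three reasons.

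- Section 15.1 does not restrict the factors to one value per person. Table 3 has Respiratory and Global Health and CESD at both weeks 4 and 6, and entered as time-varying they can move the time effect.
- Some week 6 values may be missing, as the planned multiple imputation recognises, and then even a person-level covariate shifts the estimate a little.
- Time is the only effect tested, but the model also has an intercept and a baseline slope. A baseline-to-week-4 exposure change entered with zero meaning no change would make the intercept informative, and the plan does not forbid this.

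All three stand, so the result is not forced for every listed factor. They do not rescue the analysis as written. In the first two cases what moves is a contrast between two post-switch visits. The third is a choice that the plan neither states nor points to.

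The word group might also refer to the external non-users, for whom person-level covariates could matter. The text does not exclude this, but no model in Section 15.1 includes those people. Leftover multi-arm wording is equally possible: Section 17.2 also speaks of treatment groups.

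Finally, the plan calls the trial exploratory, the analysis is supplementary, and nowhere does the plan say that it is meant as a check on changed surroundings. That purpose is my inference. These points limit the weight of the concern.

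**Conclusion.** The concern holds in a bounded form. The adjusted analysis names an effect that the single-arm model lacks. If the time effect takes its place, person-level covariates, including the two environmental scores, change the estimate by exactly zero when both visits are present. This rests only on the stated model and compound symmetry.

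Time-varying health or CESD scores, or missing week 6 data, can move it. The average sizes of about 0.15 and 0.02 on the log scale depend on the simulation's assumptions and are not predictions for this trial. In none of these cases does the time effect address whether concurrent changes explain the change from smoking baseline.

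The sentence should be corrected before analysis. The primary analysis does not depend on it.

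**What to change.** In Section 15.1:

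- Delete the reference to group and name change from baseline, log(visit/baseline), as the estimand of the adjusted analysis.
- Regress it on the change in exposure score from baseline, coded so that zero means no change and not centred at the sample mean. Report the adjusted intercept, back-transformed as the geometric mean ratio at unchanged exposure, beside the unadjusted ratio.
- Do this at week 4 only for the environmental smoke and toxicant scores, which have no week 6 value. Do it at weeks 4 and 6 for Respiratory and Global Health. If CESD is used, state that its reference value is from screening.
- State which covariates vary over time, and name the instrument meant by stress or drop the term.

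The cost is SAP wording; no new data are needed. With the 15 to 20 complete switchers considered in Section 15.2, the adjusted estimate will be imprecise, and it extrapolates if few people have unchanged exposure. Enter one or two exposures at a time and label the result exploratory. The environmental question stays unanswered at week 6.
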